6.9.5 Electrocardiography

The heart rate, QT, PR, and QRS intervals will be recorded at each assessment time. No formal inferential statistics will be applied to the ECG data.

For each post-Baseline assessment, descriptive statistics are provided for the assessment value and the change from Baseline to the assessment with mean, median, standard deviation, minimum, and maximum at each assessment time.

In addition, the number of subjects with corrected and uncorrected QT values >500 msec will be summarized. Values from individual tracings within the triplicate measurement on Day 1, time 0 hour that are >500 msec will not be included in the categorical analysis unless the average from that triplicate measurement is also >500 msec.

Electrocardiography data will be summarized by Baseline and Change from Baseline to each scheduled assessment time with descriptive statistics.

Corrections to QT intervals will be made by Fridericia's method (QTcF). Categorical analysis will be done consistent with ICH E14, "Clinical evaluation of QT/QTc interval prolongation and proarrhythmic potential for non-antiarrhythmic drugs" (October 2005).

In accordance with ICH E14, subjects will be categorized and summarized as described above according to:

- Absolute QTc interval prolongation:
 - QTc interval > 450
 - QTc interval > 480
 - QTc interval > 500
- Change from Baseline in QTc interval:
 - QTc interval increases from Baseline > 30
 - QTc interval increases from Baseline > 60.

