20. Participants demonstrating QTcF > 470 msec on Screening 12-lead ECG (confirmed with a repeat measure). Participants with known history of bundle branch block (either right or left) are allowed if QTcF value does not exceed 500 msec. Participants with a functioning pacemaker, indicated by an ECG displaying paced rhythm, are allowed with no QTcF upper limit.
21. History of diabetic ketoacidosis within the last year.
22. History of more than one severe episode of hypoglycemia that required assistance by a third party within the past year.
23. History of chronic pancreatitis.
24. Current clinically significant hepatic disease or elevated LFTs ≥ 2 times the upper limit of normal (ULN) at Screening.
25. Stage 4 kidney disease (estimated GFR < 30 mL/min/1.73 m², as calculated by the CKD-EPI equation [Levey 2009]).
26. Any laboratory value not already specified above that is outside the laboratory reference range and considered by the Principal Investigator, or appropriately qualified designee, to be a clinically significant abnormality.
27. Use of insulin therapy.
28. Any other medical condition or reason that, in the opinion of the Principal Investigator or appropriately qualified designee, makes the subject unsuitable to participate in this clinical trial.

Eligibility for randomization will be reviewed and approved by an independent Randomization Authorization Committee. The remit of this committee will be to ensure each patient deemed by the Investigator to be eligible for the trial meets key eligibility criteria and is suitable for participation in the study.

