5.2.4 ECG

12-lead ECGs are obtained at the Screening, Baseline, Month 3, Month 6/ET, and Follow-up visits. Triplicate measurements are obtained at Baseline; all other study visits collect single measurements.

ECG results will be obtained from the Central Reader. Interpretation of results as normal, abnormal not clinically significant or abnormal clinically significant will also be collected from the investigator or designee.

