8.1 Definition of Baseline

For safety evaluations, the Baseline assessment for all measurements will be the latest available, valid measurement taken prior to the initiation study medication, except for electrocardiography (ECG) values: The Baseline assessment for ECG include a triplicate assessment with the baseline value intended to be the arithmetic mean of the values taken at the Baseline assessment that are taken in triplicate. Baseline values for efficacy outcomes will be the average of screening and baseline visits where available. For the GST, the z-scores at each visit will be calculated using the mean over all patients of the average of screening and baseline, and using the standard deviation pooled across screening and baseline.

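### The absolute QTc categories in SAP 6.9.5 (>450, >480, >500 msec) have no post-Baseline condition, so read literally they mix entry ECG status with values arising after dosing

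*SAP*

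**What the plan says.** **Counting rule.** SAP 6.9.5 states that "the number of subjects with corrected and uncorrected QT values >500 msec will be summarized". Individual tracings from the Day 1, time-0 triplicate that exceed 500 msec "will not be included in the categorical analysis unless the average from that triplicate measurement is also >500 msec". Under a heading for absolute prolongation it then lists "QTc interval > 450", "QTc interval > 480" and a 500 msec row, and under a separate heading increases from Baseline of more than 30 and more than 60 msec. None of the three absolute rows is limited to post-Baseline or newly raised values.

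**Which ECG is the triplicate.** SAP 5.2.4: "Triplicate measurements are obtained at Baseline; all other study visits collect single measurements". SAP 8.1: "The Baseline assessment for ECG include a triplicate assessment with the baseline value intended to be the arithmetic mean of the values" from that triplicate.

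**Entry limits.** Criterion 20 in Protocol 4.2 begins "Participants demonstrating QTcF > 470 msec on Screening 12-lead ECG (confirmed with a repeat measure", so the general exclusion needs a confirmed value above 470. Known bundle branch block is accepted up to 500 msec. Subjects with a functioning pacemaker and paced rhythm "are allowed with no QTcF upper limit". Protocol 7.1.3 repeats these allowances, subject to there being no other cardiac exclusion.

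**Other safety data.** SAP 5.2.3 counts treatment-emergent values or changes for vital signs. SAP 5.2.5 and 6.9.4 restrict laboratory abnormalities to those normal before dosing and abnormal after. Protocol 9.8.2 discusses vital signs, ECG and laboratory results together and promises a summary of treatment-emergent abnormal values, but the SAP defines that term for laboratory values only.

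**The concern.** A count of subjects above an absolute QTc cut-off, compared by arm, is useful for drug safety only if the reader knows whether the values arose after dosing. Here the rule does not say so, and for 500 msec it explicitly admits the pre-dose average. The same number can then be both the reference for change and a countable event.

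Subjects may legitimately enter above each cut-off, so a subject whose ECG never changes can appear in an absolute row. This raises the counts in both arms, dilutes any true difference, and in a small trial lets a chance imbalance in entry ECGs look like a difference between treatments. SAP 6.9.5 plans no inferential test on ECG data, so the raw counts will be read directly.

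**Working it through.** The documents give no ECG rate to reproduce. The check is a comparison of rules, followed by an illustration whose rates are assumptions.

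**1. Is the Day 1 triplicate pre-dose?** Only Baseline is in triplicate (SAP 5.2.4) and its mean is the Baseline value (SAP 8.1). The Day 1, time-0 triplicate in SAP 6.9.5 is therefore the Baseline ECG, and an average above 500 stays in the categorical analysis. This explicit rule is written for 500 msec only. For 450 and 480 the gap is the missing post-Baseline or emergence condition.

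**2. Can a subject enter above each cut-off?**

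| Row | Who can exceed it at entry (QTcF) |
|---|---|
| >450 msec | Any subject, from above 450 to 470 |
| >480 msec | Known bundle branch block, from above 480 to 500; paced rhythm |
| >500 msec | Paced rhythm |
| Increase >30 or >60 msec | Not applicable: measured from Baseline |

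All three absolute rows can hold entry status; neither change row can.

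**3. Weight of one subject.** SAP 1.4 gives 43 enrolled with 1:1 allocation intended. The actual split is not stated; assume 22/21. Then 1/22 = 4.5% and 1/21 = 4.8%.

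**4. Number above 450 at entry.** Let p be the proportion entering above 450 (assumed). Expected number = 43 × p: 43 × 0.05 = 2.15 and 43 × 0.20 = 8.6, or about 2 to 9.

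**5. Share of an any-time count that is entry status.** Let q be the rate of newly exceeding 450 among the rest, assumed 5%. Any-time rate = p + (1 − p)q. Entry share = p / [p + (1 − p)q]. For p = 0.05: 0.05 + 0.95 × 0.05 = 0.0975, and 0.05/0.0975 = 51%.

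**6. Chance imbalance at entry.** With A ~ Bin(22, p) and B ~ Bin(21, p) independent, sum the exact probabilities over |A − B| ≥ 3.

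| p | Expected of 43 | Any-time rate (q = 5%) | Entry share (q = 5%) | Entry share (q = 10%) | P(imbalance ≥ 3) |
|---|---|---|---|---|---|
| 5% | 2.1 | 9.8% | 51% | 34% | 8% |
| 10% | 4.3 | 14.5% | 69% | 53% | 20% |
| 20% | 8.6 | 24.0% | 83% | 71% | 34% |

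A count restricted to subjects at or below 450 at Baseline would show q itself. Steps 5 and 6 concern the 450 msec row under an any-time count that includes Baseline. They say nothing about how many subjects exceed 480 or 500.

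**The case against.** **The layout may already separate Baseline.** SAP 6.9.5 says ECG data are summarised by Baseline and by change to each scheduled visit, and that the categories are summarised in the manner described earlier in the section. A by-visit table with its own Baseline column is a natural reading. This stands in part: the SAP does not rule it out, and it would remove the pre-dose values. It would not separate a subject whose QTc was long at entry and stays long, who would still be counted at Month 3 and Month 6.

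**The triplicate sentence is a safeguard.** It stops one outlying Baseline tracing from counting. That is fair as to its purpose. Its effect is still that a Baseline average above 500 counts.

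**Few subjects may be involved.** Under Protocol 7.1.3 a Baseline average above 470 holds dosing pending the central reading, and a reading confirmed as exclusionary excludes the subject. For QTcF, values above 500 at entry are essentially confined to paced rhythm. The number of such subjects could be zero. This stands, and limits the point mainly to the 450 msec row.

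**Readers have other information.** Baseline values, mean changes, the two change rows, the reviewed ECG listings and the investigator's interpretation all help to tell entry status from change. This also stands, and keeps the point minor.

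**Counting only new exceedances would lose information.** A subject going from 452 to 479 msec (+27) is already above 450, does not reach 480 and does not rise by more than 30, so would appear in no row. This is correct, and is why the absolute post-Baseline counts should be kept.

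A reader might infer that the SAP reports entry ECG status as on-study prolongation, or that all its QTc categories are affected. The documents do not support either. No text labels the absolute counts as on-study or treatment-emergent, and two of the five categories are referenced to Baseline.

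**Conclusion.** The point holds for the three absolute QTc rows on the literal, subject-level reading. They have no post-Baseline or emergence condition, the 500 msec rule keeps a pre-dose average, and the entry rules allow subjects in above every cut-off. The SAP uses treatment-emergent definitions for laboratory values and vital signs but gives ECG none.

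The firm size is that one subject is 4.5 to 4.8 percentage points of an arm, given an assumed 22/21 split. The 2 to 9 subjects above 450, the 51 to 83% entry share (at q = 5%) and the 8 to 34% chance of an imbalance of three or more rest on an assumed 5 to 20% prevalence that the documents do not give. They show what could happen, not what did, and do not establish a false or hidden QT signal. The tables are descriptive and no efficacy conclusion depends on them. Severity: a worthwhile refinement, not a serious flaw.

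**What to change.** In SAP 6.9.5:

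- State that the absolute category counts use post-Baseline values only.
- Show the Baseline triplicate mean in its own row by arm, outside the on-study count, and reword the triplicate sentence to match.
- Keep the post-Baseline absolute counts, and add for each cut-off the number of subjects at or below it at Baseline and above it after dosing, with those at or below it at Baseline as denominator. A shift table from Baseline category to worst post-Baseline category would serve equally well.
- Flag or list paced-rhythm and bundle-branch-block subjects separately.

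The cost is some SAP wording, one extra table and slightly more programming. No assessment, eligibility criterion or clinical rule changes.

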6.10 Pharmacokinetics Analysis

Data resulting from blood sampling for trough concentrations of TTP488 and metabolites will be analyzed descriptively.

No formal inferential statistics will be applied to the pharmacokinetic data.

6.11 Pharmacodynamic Analysis

Plasma inflammatory biomarker change from baseline to 3 and 6 months will be evaluated using an MMRM containing terms for baseline value, treatment, time, and treatment-by-time interaction. Analysis will be done separately for each biomarker.

6.12 Concomitant Medications

Concomitant medications will be summarized by drug category and listed. Summaries will also be prepared for individuals taking medications for the treatment of hypertension and diabetes. Hypertension summaries will be stratified by Y/N while diabetes summaries will be stratified according to type of medication classified under the concomitant medications ATC4 variable. Use of these medications in addition to, Acetylcholinesterase and Memantine usage at baseline will be included in baseline tables. Summaries will be provided overall and stratified by treatment group.

7 COVID-19 Data and Analysis Conventions

Regulatory guidance was issued by the FDA and the EMA to acknowledge the potential impact of the COVID-19 pandemic on clinical trials, including missed visits or evaluations done in a manner different from the original intention of the protocol. This SAP includes recommended plans for coping with statistics and data issues related to COVID-19.

From the FDA guidance, the following excerpt applies to this SAP:

Sponsors should describe in appropriate sections of the clinical study report (or in a separate study-specific document):

1. Contingency measures implemented to manage study conduct during disruption of the study as a result of COVID-19 control measures.
2. A listing of all participants affected by the COVID-19 related study disruption by unique subject number identifier and by investigational site, and a description of how the individual's participation was altered.
3. Analyses and corresponding discussions that address the impact of implemented contingency measures (e.g., trial participant discontinuation from investigational product and/or study, alternative procedures used to collect critical safety and/or efficacy data) on the safety and efficacy results reported for the study.

Robust efforts by sponsors, investigators, and IRBs/IECs to maintain the safety of trial participants and study data integrity are expected, and such efforts should be documented. As stated above, FDA recognizes that protocol modifications may be required, including unavoidable protocol deviations due to COVID-19 illness and/or COVID-19 control measures. Efforts to minimize impacts on trial integrity, and to document the reasons for protocol deviations, will be important.

The following modifications to the primary analysis are intended to reflect the original analysis plan accommodating emergency modifications to visit schedules:

- Visits were intended to result in the primary endpoint evaluation at Month 6. Due to COVID-19, the endpoint visit may be later than Month 6. Three approaches will be used:
 - In the primary analysis, the Month 6 value can be predicted from earlier or later time points. Multiple imputation methods will be employed to predict all missing Month 6 visits, based on available time points for each patient.
 - Supportive analysis will be done using MMRM, which copes with extra data or mis-timed data.
 - Supportive analysis will also be done using the latest on-treatment value available, regardless of whether it is earlier or later than Month 6.
- Homogeneity analysis will be done comparing results prior to COVID-19 with those after impact of COVID-19 started. COVID-19 impact start date will be 13 March 2020.

8 Data Conventions

The following analysis conventions will be used in the statistical analysis.

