6.2 Statistical Methodology for Efficacy Analysis

The primary analysis will use the ITT methodology and a mixed-model measures (MMRM) methodology with a random slope and intercept for each individual. The MMRM will utilize an

unstructured covariance with only one parameter for the correlation between the slope and intercept. Time (ADY) is considered as a continuous variable. Analysis will include baseline risk score, treatment, time, as well as HbA1C by treatment, treatment-by-time, baseline by treatment, and baseline by time interactions as fixed effects. Subject will be included as a random effect. Baseline visit will be included in the model. Baseline risk score is derived from the historic STEADFAST data and calculated as a linear calculation of:

$$age*-0.03582 + hba1c*-0.2335 + mmsebl*-0.2683 + base*-0.09342$$

First the baseline risk score will be subtracted from the change score for each individual. Then the mean baseline value of the risk adjusted change score will be calculated separately for each treatment group. Finally, the risk adjusted change scores for each individual will have their group mean added back in to ensure an average score of 0 at baseline for each group. This adjusted change score will be used in the model in place of change from baseline. Model assumptions will be evaluated. If the parametric assumptions are evaluated as inappropriate or violated, rank analogues will be advanced.

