6.6 Statistical Methodology for Primary Efficacy Analysis

We will use $\alpha = 0.0499$, which includes an adjustment of 0.0001 for interim analyses performed by the Independent Data Monitoring Committee (IDMC).

In addition to the primary MMRM model, a last z-score carried forward (LZCF), will be run for the primary variable. Z-scores will be calculated for each timepoint. For individuals with missing data the last z-score will be carried forward. Let Z be the imputed z-score, while x is the last observation at timepoint t_1 and μ and σ are the mean and standard deviation of the next timepoint (t_2) for which the data is missing.

$$Z_{t2} = (x_{t1} - \mu_{t2}) / \sigma_{t2}$$

Z-scores imputed relative to the group mean and standard deviation at each timepoint, will better preserve the slope of each arm and thus is more robust to differences in dropout rate across treatment. The model using LZCF will be the primary analysis for the GST and the composite scores..

Descriptive summaries will be produced of the observed values and change from Baseline in ADAS-cog14 by treatment group at each individual time point and at endpoint (final on-treatment assessment for each subject).

For statistical analyses, 95% confidence intervals will be produced for the least-squares means (LSM) in each treatment group, as well as the LSM differences as compared to placebo. For MMRM and ANCOVA, two-sided p-values will be displayed for the comparison against placebo.

The primary analysis controls alpha through the conditional sequence of hypothesis testing. No further adjustment for multiplicity is necessary.

If the PPS differs from the FAS by more than 15%, the analyses will be replicated on the PPS. If the PPS and the FAS do not differ by more than 15%, analysis may not be done on the PPS. Final judgments will be made at the blind data review meeting in accordance with ICH E9.

6.6.1 PK

The trough PK concentration data collected prior to each dose will be used in a concentration response relationship analysis to assess correlation with each outcome which will mirror the primary analysis but replace the treatment variable with PK concentration.

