6.6.2 Missing Data

An essential component of the thorough analysis includes an assessment of the impact of missing data on study conclusions. As a part of assessing this impact, supportive analysis will include:

- observed cases by assessment time.

To ensure robustness of analysis conclusions against missingness, multiple imputation methods will also be done to cope with missing data as a key supportive analysis using the final on-treatment assessment of treatment failures as non-missing data at endpoint. Multiple imputations (MI) will be used as a supportive analysis with 100 invocations (acknowledging that more invocations are needed with more missing data). Monte Carlo methods are planned.

In accordance with the recommendations of the report from the National Academy of Science (NAS) panel “*The Prevention and Treatment of Missing Data in Clinical Trials*,” (National Research Council, 2010), missingness is classified as “missing at random” (MAR) or “missing not at random” (MNAR). When subjects are withdrawn due to treatment failure, this event is considered in this sensitivity analysis to be MNAR, and the endpoint value is taken as the hard endpoint (imputed for progression over time) in analysis. Data that are missing for other reasons are considered to be MAR, and standard multiple imputation methods are planned.

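### The SAP names two different primary analyses for ADAS-cog14 in Part 1 (MMRM in 6.2 and 6.6, multiple imputation in section 7), and its 6.4 significance rule cannot be applied to Part 1

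*SAP*

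**What the plan says.** **MMRM as primary.** SAP 6.2: "The primary analysis will use the ITT methodology and a mixed-model measures (MMRM) methodology", with a random slope and intercept per subject; "Time (ADY) is considered as a continuous variable". SAP 6.6 agrees: "In addition to the primary MMRM model, a last z-score carried forward (LZCF), will be run for the primary variable". SAP 6.6.2 gives MI the secondary role: "Multiple imputations (MI) will be used as a supportive analysis with 100 invocations".

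**MI as primary.** SAP section 7 opens its list with "The following modifications to the primary analysis are intended to reflect the original analysis plan accommodating emergency modifications to visit schedules". Its first item, for the primary analysis, is "Multiple imputation methods will be employed to predict all missing Month 6 visits, based on available time points for each patient". The second is "Supportive analysis will be done using MMRM, which copes with extra data or mis-timed data". The third, also supportive, uses the latest on-treatment value.

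**Alpha and success rule.** SAP 6.6 sets alpha at 0.0499, "which includes an adjustment of 0.0001 for interim analyses performed by the Independent Data Monitoring Committee". SAP 6.4 declares significance at p < 0.049 on two primary endpoints in both an A-study and a B-study. SAP section 2 gives Part 1 a single primary endpoint. SAP 5.1.4 uses 0.05 to decide when the composites and the GST are assessed. SAP 1.7 allows the IDMC up to ten analyses at 0.0001 each.

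**Protocol.** The synopsis makes an MI-based ANCOVA primary, supported by MMRM. Section 9.7.2 makes MMRM primary, with time as a class variable, and MI supportive. For Part 1, section 9.14 allows at most four IDMC analyses sharing 0.0001.

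**The concern.** An SAP should leave one analysis and one threshold for the primary hypothesis. Here the MMRM p-value and the MI p-value can each be presented as the primary ADAS-cog14 result with a section of the SAP to cite. With 43 subjects enrolled, two ways of handling missing Month 6 data could fall on opposite sides of the threshold. If that is not settled before unblinding, the choice can be made after both results are known. H01 also gates the hypotheses on A-IADL, CDR-sb and FAQ, so the ambiguity carries down the sequence.

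The MI version cannot be run as written, because section 7 does not say what model is fitted to the completed data. The sentence in 6.4 that should define success describes a different pair of studies: the protocol (1.1.3) identifies the A-study and B-study as the earlier Phase 3 trials.

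**Working it through.** **1. Roles side by side**

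| Source | MMRM | MI |
|---|---|---|
| SAP 6.2, 6.6 | primary | not mentioned |
| SAP 6.6.2 | not mentioned | supportive |
| SAP 7 | supportive | primary |
| Protocol synopsis | supportive | primary (with ANCOVA) |
| Protocol 9.7.2 | primary | supportive |

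The MI in section 7 covers every missing Month 6 visit, not only those missed because of COVID-19. SAP 1.9 lists neither this switch nor the move from class time (protocol 9.7.2) to continuous time with random slopes (SAP 6.2).

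**2. Alpha arithmetic**

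- Part 1 (protocol 9.7.2 and 9.14, SAP 6.6): 0.05 − 0.0001 = 0.0499.
- Part 2 (protocol 9.7.2 and 9.14): 10 × 0.0001 = 0.001, and 0.05 − 0.001 = 0.049.

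So the threshold in SAP 6.4 and the ten-look budget in SAP 1.7 both match the protocol's Part 2 rule.

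**3. Effect of the threshold on power**

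Inputs from SAP 1.6: difference 1.54, SD 3.4, N = 43. I assumed a 22/21 split.

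- SE = 3.4 × √(1/22 + 1/21) = 1.037; noncentrality = 1.54 / 1.037 = 1.485; df = 41.
- Noncentral t, two-sided alpha 0.05: power 30.5%, and p = 0.145 if the assumed effect and SD are observed. The SAP states 30% and 0.144, so its figures reproduce.
- Alpha 0.0499: 30.5%. Alpha 0.049: 30.2%.

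**4. Type I error if either analysis could be claimed as primary**

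The critical value for two-sided alpha 0.0499 is 1.961. For two standard normal statistics with correlation ρ, the error rate is 1 − P(|Z1| ≤ 1.961 and |Z2| ≤ 1.961). The last column is the same calculation for three equally correlated statistics. It applies only if the last-z-score-carried-forward (LZCF) run could also reject H01.

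| ρ (assumed) | MMRM or MI | MMRM, MI or LZCF |
|---|---|---|
| 0.99 | 5.65% | 6.0% |
| 0.97 | 6.1% | 6.8% |
| 0.95 | 6.4% | 7.3% |
| 0.90 | 7.0% | 8.3% |
| 0.80 | 7.8% | 9.8% |

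No document gives these correlations, so the rows are a range and not estimates.

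**The case against.** **Section 7 may be a deliberate COVID-19 override.** That is possible, and a specific section would normally qualify a general one. But 6.2, 6.6 and 6.6.2 were left unchanged, 1.9 does not list the override, and no model is given for the imputed data. SAP 8.2 is the nearest thing to a precedence rule, and it can be read either way. It bars imputation of clinical data unless explicitly defined, so section 7 could be the exception. It also says that primary methods are not subject to change, which favours 6.2.

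**The SAP supersedes the protocol.** It does, under protocol 9.0 and SAP 1.9. That removes the protocol as a tie-breaker, and the protocol is itself split. It does not resolve a conflict inside the SAP.

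**A reader might infer that LZCF is a third route to H01.** The section 2 footnote goes on to the composites and GST only when neither ADAS-Cog run is significant, which could suggest that a significant LZCF counts. The documents do not establish this. SAP 6.6 describes LZCF as run in addition to the primary MMRM and makes it primary only for the GST and composites. The footnote governs when proof of concept is assessed, not what rejects H01. Figure 1, the hypothesis schematic, is not shown and may settle the question.

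**A reader might infer that Part 1 has no usable success criterion.** That goes too far. H01 together with the 6.6 alpha is an operable test once the analysis is named, and protocol 9.7.5 has a plain rule at 0.05. The 6.4 sentence is evidently carried over and offers no workable competing threshold. The 0.05 in SAP 5.1.4 is also minor, since protocol 9.7.2 treats 0.0499 and 0.05 as practically the same.

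**Conclusion.** The contradiction over the primary analysis is established from the SAP text alone, and the 6.4 rule does not describe Part 1. Both should be fixed.

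The size is modest. Type I error for H01 would be about 5.65% to 7.8% instead of 4.99%, if either analysis could be claimed and the correlation lies between 0.80 and 0.99. The three-test range of 6.0% to 9.8% holds only under the contested LZCF reading. The threshold mismatch costs 0.3 percentage points of power.

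The consequence is limited further because Part 1 is a learning stage, and because section 2 allows other routes to proof of concept, which are a separate issue. It still matters: Part 1 informs the endpoint and sample size for Part 2, and the SAP is written to support product registration.

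**What to change.** Before unblinding, change the SAP wording as follows.

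1. **Name one primary analysis throughout.** The least change is to keep the 6.2 MMRM, which uses actual study day, so late visits enter at their true time. In section 7, relabel MI and the latest on-treatment value as sensitivity analyses, and state the model for the imputed data, for example ANCOVA of Month 6 change on treatment and baseline ADAS-cog14, in line with the protocol synopsis. If section 7 was meant as an override, amend 6.2, 6.6 and 6.6.2 instead and state its model there.
2. **Replace the 6.4 sentence with a Part 1 rule.** Part 1 is statistically significant if the treatment difference in ADAS-cog14 change at Month 6 (Day 180), from the named primary analysis, favours azeliragon with two-sided p < 0.0499. Use 0.0499 in 5.1.4, and align 1.7 with the protocol's Part 1 IDMC rule.
3. **Settle LZCF.** Confirm in the section 2 footnote, consistent with 6.6 and Figure 1, that LZCF of ADAS-cog14 is a sensitivity analysis and cannot by itself reject H01.
4. **List the change of primary model in 1.9**, relative to both the synopsis and protocol 9.7.2.

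No extra data are needed. The sponsor gives up alternative routes to H01. If the MMRM is kept, the Day 180 estimate relies on linear change over time, which the MI-based sensitivity analysis can help check once its model is stated.
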